##### 3.1.1. Dose Escalation Reviews

The primary driver for the dose escalation decisions in Part 1 will be the incidence rate of DLT and other adverse events (AEs) of each dose cohort. The study uses Neuenschwander Continual Reassessment Method (N-CRM) [Neuenschwander, 2008] to guide dose escalation. An updated posterior estimate of the dose-toxicity curve will also be provided at the time of the dose-escalation meeting and the Dose Escalation Committee (DEC) will review all available data and decide if safe to escalate the dose.

The N-CRM design makes use of a Bayesian logistic regression model relating dose and toxicity and makes use of DLT information from all doses. The N-CRM estimates, for each potential dose, the posterior probabilities that the DLT rate lies in each of four toxicity ranges:

- A dose falls in the **Under-dosing** range if the probability of a DLT at the dose is <16%.
- A dose falls in the **Target** Toxicity range if the probability of a DLT at the dose is  $\geq 16\%$  and < 33%.
- A dose falls in the **Excessive** Toxicity range if the probability of a DLT at the dose is  $\geq 33\%$ , and <60%.
- A dose falls in the **Unacceptable** Toxicity range if the probability of a DLT at the dose is  $\geq 60\%$ .

At the time of each dose-escalation decision, the dose with the highest posterior probability of lying in the Target Toxicity range will be the model-recommended dose for the next cohort. Additionally, the following constraints for the recommended dose will be maintained:

- The posterior probability of the DLT rate lying in the Excessive Toxicity or Unacceptable Toxicity range is less than 25%.
- VTE safety rules
  - Upon re-initiation of enrolment under Protocol Amendment 3, details of a VTE meeting the DLT criteria are given in Section 4.1.3 and in Table 6.

- Upon re-initiation of enrolment under Protocol Amendment 3 at 100mg , dose escalation steps will be considered in maximal steps of 50 mg, depending on the pharmacodynamic effects and the safety profile observed in previous cohorts, taking into consideration the updated DLT criteria.
- Note: GSK3368715 dose de-escalation is also possible using this method.

An updated posterior estimate of the dose-toxicity curve will also be provided at the time of the dose-escalation meeting. Further details about the N-CRM approach are provided in Section 9 of Protocol Amendment 3. Although the N-CRM will be used to recommend the next dosing level, the DEC (i) will review all available data, including safety, PK and PD data from current and prior cohorts, (ii) can halt or reduce the GSK3368715 dose based on clinical judgement at any time during the trial, and (iii) can recommend alternative schedule(s) if emerging data suggest that continuous daily dosing will result in excessive toxicity or limited efficacy. Note: if an alternative schedule is evaluated, the starting dose at the time of a schedule change will be the dose for which the target toxicity level was not exceeded using once daily dosing schedule.

#### **3.1.1.1. Displays to Be Created for Dose Escalation Review**

For dose escalation decisions, ongoing data review will be primarily based on Tibco Spotfire Clinical Graphics (web-based data visualization tool). The following three listings will be created by Statistics and Programming group. The analysis will be based on the All-Treated Population.

- Listing of All Adverse Events
- Listing of Any Grade 2 and Above Lab Tests or Any Abnormal Lab Tests if Not Gradable
- Listing of Exposure to GSK3368715

For the first dose escalation meeting, only spreadsheets containing relevant study data will be supplied. For subsequent dose escalation meetings, SDTM datasets will be available and the two listings above may be provided. The Data Surveillance Tool may be used to create data visualizations to facilitate review.

Details of the planned displays are presented in [Appendix 10: List of Data Displays](#).

#### **3.1.2. Recommended Phase 2 Dose (RP2D) Analysis**

The Dose Escalation Committee (DEC) evaluated the DL100mg cohort and deemed it safe, but upon review of the cumulative safety, efficacy, PK and PD data, GSK decided that no further enrolment will take place on the study. As a result, all analyses corresponding to Part 2, as well as the Exploratory Objectives for both Part 1 and Part 2, will not be performed. However, all other Part 1 analyses will be performed.

RP2D of GSK3368715 was planned to be determined after review of all available safety-, PK-, PD-, and clinical efficacy data in accordance with the N-CRM design. The RP2D was planned to be equivalent with the MTD or a lower GSK3368715 dose that provides adequate PK exposure and biologic activity with superior tolerability.

### **3.1.2.1. Displays to Be Created for RP2D Analysis**

The Dose Escalation Committee (DEC) evaluated the DL100mg cohort and deemed it safe, but upon review of the cumulative safety, efficacy, PK and PD data, GSK decided that no further enrolment will take place on the study. As a result, all analyses corresponding to Part 2, as well as the Exploratory Objectives for both Part 1 and Part 2, will not be performed. However, all other Part 1 analyses will be performed.

### **3.1.3. Interim futility analyses (IFA) Analyses**

The Dose Escalation Committee (DEC) evaluated the DL100mg cohort and deemed it safe, but upon review of the cumulative safety, efficacy, PK and PD data, GSK decided that no further enrolment will take place on the study. As a result, all analyses corresponding to Part 2, as well as the Exploratory Objectives for both Part 1 and Part 2, will not be performed. However, all other Part 1 analyses will be performed.

## **3.2. Final Analyses**

The Dose Escalation Committee (DEC) evaluated the DL100mg cohort and deemed it safe, but upon review of the cumulative safety, efficacy, PK and PD data, GSK decided that no further enrolment will take place on the study. As a result, all analyses corresponding to Part 2, as well as the Exploratory Objectives for both Part 1 and Part 2, will not be performed. However, all other Part 1 analyses will be performed.

The final Part 1 analyses will be performed after all required database cleaning activities have been completed and Database Release (DBR) and Database Freeze (DBF) have been declared by Data Management.

## 4. ANALYSIS POPULATIONS

| Population           | Definition / Criteria  | Analyses Evaluated   |
|----------------------|--|--|
| Screened             | 
 
All participants who were screened for eligibility
 
   | 
 
Study Population
 
   |
| Evaluable            | 
 
All participants who have had Week 24 disease assessments, have progressed or died, or permanently discontinued from the study intervention.
 
 |  |
| All-Treated          | 
 
All participants who received at least one dose of GSK3368715.
 
   | 
 
Study Population
 
Final Efficacy
 
Safety
 
 |
| Pharmacokinetic (PK) | 
 
Participants in the All-Treated population from whom at least one PK sample was obtained, analysed, and was measurable.
 
                      | 
 
PK
 
   |

Refer to [Appendix 10](#): List of Data Displays which details the population used for each display.

### 4.1. Protocol Deviations

Important protocol deviations (including deviations related to study inclusion/exclusion criteria, conduct of the trial, patient management or patient assessment) will be summarized and all protocol deviations, including both important and non-important, will be listed.

Protocol deviations will be tracked by the study team throughout the conduct of the study in accordance with the Protocol Deviation Specifications developed by PAREXEL.

- Data will be reviewed prior to freezing the database to ensure all deviations are captured and categorized on the protocol deviations dataset.
- This dataset will be the basis for the summaries and listings of protocol deviations.

A separate listing of all important inclusion/exclusion criteria deviations will also be provided. This summary will be based on data as recorded on the inclusion/exclusion page of the eCRF.

There is no Per-Protocol Population for this study. Protocol deviations will not be used to determine membership in any particular study population for this study.

## 5. CONSIDERATIONS FOR DATA ANALYSES AND DATA HANDLING CONVENTIONS

### 5.1. Study Treatment & Sub-group Display Descriptors

This is a single-arm, dose escalation and expansion study of GSK3368715. Data will be listed and summarized per the GSK reporting standards whenever applicable. In Part 1 data will be listed and summarized by dose levels.

| Treatment Group Descriptions |              |
|------------------------------|--------------|
| Data Displays for Reporting  |              |
| Description                  | Order in TLF |
| GSK3368715 50mg              | 1            |
| GSK3368715 100mg             | 2            |
| GSK3368715 200mg             | 3            |

### 5.2. Reporting Conventions

- Unless otherwise specified, the denominator in percentage calculation at each scheduled visit will be based on the number of subjects with a non-missing value at each particular visit.
- All data are reported according to the dose/regimen initially received by the subject.
- Data will be listed by treatment group, site ID, and subject.
- Planned times relative to investigational product dosing will be used in all summary tables and figures.
- Actual, rather than planned, sampling times will be used in the derivation of PK parameters and in the individual concentration-time plots. Planned times will be used in the descriptive summaries and in mean and median plots. Listings of PK concentration-time data will be done by actual sampling times relative to dosing time.
- Unless stated otherwise, descriptive summaries will include n, mean, standard deviation (SD), median, minimum and maximum for continuous variables and n and percent for categorical variables. Display minimum and maximum in the same precision as data was collected, mean and median using 1 additional decimal place, and SD using 2 additional decimal places.
- This is a multicenter study. Data from all study sites will be integrated and no controlling for site-effect will be considered in the statistical analyses.
- Analyses are to be performed using the SAS System, Version 9.4 or higher. Programs will be imported into HARP and the final output will be produced by running drivers in HARP. Some graphics may be produced using the TSCG (Tibco Spotfire Clinical Graphics) - comprising of S-Plus (R) 7.0.6 or higher.
- Deviations from the analyses in the RAP will be identified in the final CSR.

### 5.3. Baseline Definitions

For all endpoints (except as noted in baseline definitions) the baseline value will be the latest pre-dose assessment within 14 days prior to first dose with a non-missing value, including those from unscheduled visits. For laboratory data, baseline will be the latest non-missing pre-dose value from central lab. If there are multiple assessments on the same day, the mean will be used as the baseline value. If a subject has an Unscheduled visit for Day 1, collected on the same date as a scheduled visit for Day 1, the planned Day 1 takes precedence over the Day 1 unscheduled visit.

For ECG analyses, subject level baseline is defined as the mean of triplicate baseline assessments.

For subjects who did not receive any study intervention during the study, baseline will be defined as the latest, non-missing collected value.

Unless otherwise stated, if baseline data is missing, no derivation will be performed and baseline will be set to missing.

| Parameter                     | Study Assessments Considered as Baseline             |                  | Baseline Used in Data Display |
|-------------------------------|--|------------------|-------------------------------|
|                               | Screening
(within 14 days prior
to first dose) | Day 1 (Pre-Dose) |                               |
| Efficacy               |  |                  |                               |
| Target and non-target lesions | X  |                  | Screening visit               |
| Safety                 |  |                  |                               |
| Laboratory                    | X  | X                | Latest up to Day 1            |
| Vital Signs                   | X  | X                | Latest up to Day 1            |
| ECG*                          | X  | X                | Latest up to Day 1            |

\*Average of triplicate assessments to be used.

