8.2.4. Holter Monitoring

Digital Holter ECG data will be obtained from 12-lead continuous Holter monitoring device supplied by the Sponsor. ECG acquisition via the Holter monitoring device will be performed at planned time points indicated in the SoA (Section 1.3) and should be obtained prior to phlebotomy and vital sign time points.

Analysis of intervals and morphology from the continuous digital ECG data will be acquired and stored electronically for all on-intervention timepoints. The 24 hour screening Holter to determine eligibility will be manually over-read by an external central validated ECG laboratory. In cases with equivocal findings a site cardiologist may aid in determining eligibility.

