8.2.6. Clinical Safety Laboratory Assessments

- Refer to [Appendix 2](#) for the list of clinical laboratory tests to be performed and to the SoA for the timing and frequency.
- The investigator must review the laboratory report, document this review, and record any clinically relevant changes occurring during the study in the AE section of the CRF. The laboratory reports must be filed with the source documents. Clinically significant abnormal laboratory findings are those which are not associated with the underlying disease, unless judged by the investigator to be more severe than expected for the participant's condition.
- All laboratory tests with values considered clinically significantly abnormal during participation in the study or within 30 days after the last dose of study

intervention should be repeated until the values return to normal or baseline or are no longer considered significantly abnormal by the investigator or Medical Monitor.

- If such values do not return to normal/baseline within a period of time judged reasonable by the investigator, the etiology should be identified and the sponsor notified.
- All protocol-required laboratory assessments, as defined in [Appendix 2](#), must be conducted in accordance with the laboratory manual and the SoA.

Laboratory requisition forms must be completed and samples must be clearly labeled with the participant number, protocol number, site/center number, and visit date. Details for the preparation and shipment of samples will be provided by the laboratory and are detailed in the SRM. Reference ranges for all safety parameters will be provided to the site by the laboratory responsible for the assessments.

If additional non-protocol specified laboratory assessments are performed at the institution's local laboratory and result in a change in participant management or are considered clinically significant by the investigator (e.g., SAE or AE or dose modification) the results must be recorded in the eCRF.

Refer to the SRM for appropriate processing and handling of samples to avoid duplicate and/or additional blood draws.

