8.9.4. MTAP testing

A requirement for inclusion in the study is the availability of archival tumor tissue, or willingness to undergo a fresh biopsy to determine MTAP status.

In part 1, MTAP testing will be performed retrospectively.

In Part 2, prospective MTAP testing is required to confirm MTAP deficiency for enrolment unless local MTAP or *CDKN2A* results are available. In this latter situation, central MTAP testing will be used to confirm MTAP deficiency.

Additionally, SDMA IHC may be conducted to correlate MTAP expression level and SDMA level with response.

Screen failure tissue, used for central testing will be retained. This tissue may be used in the validation of potential diagnostic assays to detect MTAP.

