10.1.7. Data Quality Assurance

- All participant data relating to the study will be recorded on printed or electronic CRF unless transmitted to the sponsor or designee electronically (eg, laboratory data). The investigator is responsible for verifying that data entries are accurate and correct by physically or electronically signing the CRF.
- The investigator must maintain accurate documentation (source data) that supports the information entered in the CRF.
- The investigator must permit study-related monitoring, audits, IRB/IEC review, and regulatory agency inspections and provide direct access to source data documents.
- Monitoring details describing strategy (e.g., risk-based initiatives in operations and quality such as Risk Management and Mitigation Strategies and Analytical Risk-Based Monitoring), methods, responsibilities and requirements, including

handling of noncompliance issues and monitoring techniques (central, remote, or on-site monitoring) are provided in the Monitoring Plan.

- The sponsor or designee is responsible for the data management of this study including quality checking of the data.
- The sponsor assumes accountability for actions delegated to other individuals (e.g., Contract Research Organizations).
- Study monitors will perform ongoing source data verification to confirm that data entered into the CRF by authorized site personnel are accurate, complete, and verifiable from source documents; that the safety and rights of participants are being protected; and that the study is being conducted in accordance with the currently approved protocol and any other study agreements, ICH GCP, and all applicable regulatory requirements.
- Records and documents, including signed ICF, pertaining to the conduct of this study must be retained by the investigator for 25 years from the issue of the final clinical study report (CSR)/ equivalent summary unless local regulations or institutional policies require a longer retention period. No records may be destroyed during the retention period without the written approval of the sponsor. No records may be transferred to another location or party without written notification to the sponsor.

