10.2. Appendix 2: Clinical Laboratory Tests

- The tests detailed in [Table 11](#) will be performed by the local laboratory.
- Protocol-specific requirements for inclusion or exclusion of participants are detailed in Section 5 of the protocol.
- Additional tests may be performed at any time during the study as determined necessary by the investigator or required by local regulations.
- Pregnancy Testing

Refer to Section [5.1](#) Inclusion Criteria for screening pregnancy criteria.

- Pregnancy testing (urine or serum as required by local regulations) should be conducted at monthly intervals during intervention

Table 11 Protocol-Required Safety Laboratory Assessments

Laboratory Assessments	Parameters			
Hematology	Platelet Count	RBC Indices: MCV MCH %Reticulocytes		WBC count with Differential: Neutrophils Lymphocytes Monocytes Eosinophils Basophils
	RBC Count			
	Hemoglobin			
	Hematocrit			
Clinical Chemistry ¹	BUN	Potassium	AST (SGOT)	Total and direct bilirubin
	Creatinine	Sodium	ALT (SGPT)	Total Protein
	Glucose	Calcium	Alkaline phosphatase	Albumin
	Lipase	Amylase		
Coagulation	PTT, PT/INR			
Routine Urinalysis	
 • Specific gravity • pH, glucose, protein, blood, and ketones by dipstick • Microscopic examination (if blood or protein is abnormal) 			
Other Screening Tests	
 • Highly sensitive serum or urine Beta human chorionic gonadotropin (βhCG) pregnancy test (as needed for women of childbearing potential)² • Serology (HIV antibody, HBsAg, and hepatitis C virus antibody) • Cardiac Troponin I or TroponinT (local standard, no point-of-care assay) 
The results of each test must be entered into the CRF.
			

Abbreviations: ALT = alanine aminotransferase; AST = aspartate aminotransferase; β hCG = beta-human chorionic gonadotropin; BUN = blood urea nitrogen; HBsAg = Hepatitis B surface antigen; MCH = mean corpuscle haemoglobin; MCV = mean corpuscle volume; RBC = red blood cells; SGOT = serum glutamic-oxaloacetic transaminase; SGPT = serum glutamic-pyruvic transaminase; WBC = white blood cells

NOTES :

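### SAP 5.3 takes laboratory baseline only from a central laboratory, but protocol Appendix 2 has the same tests done locally; a participant with no central pre-dose value loses baseline or is counted as grade 0

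*SAP*

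**What the plan says.** On the source of the baseline value, SAP 5.3 reads: "For laboratory data, baseline will be the latest non-missing pre-dose value from central lab". The table in the same section accepts a screening or a Day 1 pre-dose assessment. The section gives no alternative for a participant who has no central value, and it leaves baseline missing when there is nothing to use.

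Protocol Appendix 2 says that the tests in its Table 11 "will be performed by the local laboratory". SAP Table 1 (section 8.5) lists the same panels.

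The central work that the protocol does describe is of other kinds. The screening Holter recording is "manually over-read by an external central validated ECG laboratory" (8.2.4). Where local results were used for Part 2 enrolment, "central MTAP testing will be used to confirm MTAP deficiency" (8.9.4).

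Protocol 8.2.6 is less clear. Required tests "must be conducted in accordance with the laboratory manual and the SoA", and the section also speaks of requisition forms, shipping of samples and reference ranges sent to the site by the laboratory. Its only mention of the institution's local laboratory is in a sentence that begins "If additional non-protocol specified laboratory assessments are performed".

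Protocol section 8 also allows results from routine care obtained before consent, with blood count as its example, to serve as screening or baseline values if they meet the protocol's criteria and timing.

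**The concern.** Read together and followed literally, the two documents leave laboratory baseline with no source. The SAP accepts central values only, while the protocol sends the tests to local laboratories. SAP 2.1, which lists changes from the protocol's planned analysis, mentions no change of laboratory source.

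All the planned laboratory summary tables compare later values with baseline. If baseline is lost, the change tables lose content. The grade tables fail in a different way: they still fill, but with a starting grade of 0 that nobody observed. Dose groups in Part 1 are small (the SAP gives 3 to 12 participants per level), so a single false grade shift would be visible in a table.

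**Working it through.** No sample size, power or error rate is involved. The check sets the texts side by side and follows one participant through the SAP's rules.

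**1. Source of the value**
- Baseline: central laboratory only (SAP 5.3).
- Where the tests are run: local laboratory (protocol Appendix 2).
- Central haematology or chemistry laboratory named: none in either document.
- Fallback to local values: none in the SAP.

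**2. Result when no central pre-dose value exists**
- Baseline is left missing (SAP 5.3).
- Change and percentage change are then missing (SAP 14.6.1).
- An absent baseline grade is counted as grade 0 (SAP 8.5).
- Baseline status against the normal range is unavailable. The SAP text gives no specific rule for this; the display standard that it cites may give one.

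**3. Tables exposed (SAP 14.10.5)**
- Change from baseline: 3.10 (chemistry) and 3.13 (haematology).
- Grade change: 3.11 and 3.14.
- Change relative to normal range: 3.12 and 3.15.
- Count: 2 + 2 + 2 = 6, which is every planned laboratory summary table. This counts displays; it is not an effect size.

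**4. Illustration**
The ALT entry limit is 2.5 x ULN (protocol 5.1). Take ALT at 2.0 x ULN both before dosing and on Day 8. The participant is eligible (2.0 ≤ 2.5) and above the normal range (2.0 > 1.0). Let g be the toxicity grade of that value. The CTCAE table is not in the documents, so g is an assumption.
- With the local baseline used: change = 2.0 − 2.0 = 0; grade shift = g − g = 0.
- As the SAP is written, with no central value: change is missing; grade shift = g − 0 = g.
- Error in the grade table: 0 steps if g = 0, 1 step if g = 1, 2 steps if g = 2.

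ALT is only an example. Protocol 5.1 sets no entry limit for AST, alkaline phosphatase, amylase, lipase or glucose, and it allows isolated bilirubin above 1.5 x ULN by exception.

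**5. Share of participants**
Protocol 2.2.1.4.3 gives 19 participants dosed by Amendment 3. The affected share lies between 0/19 = 0% and 19/19 = 100% of these, plus any enrolled later. The documents do not narrow this range.

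**6. Could only some participants be affected?**
Yes, even if a central laboratory was used. Routine-care results may serve as baseline (protocol section 8), and Day 1 laboratory tests may be skipped when screening samples were drawn on Day −3 to Day −1 (footnote to protocol Table 2). A baseline that is valid under the protocol could therefore be a local result that SAP 5.3 would not accept.

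**The case against.** The strongest reply is that a central laboratory probably existed and that Appendix 2 holds the error. Protocol 8.2.6 reads like instructions for an off-site laboratory. Appendix 2 also marks particular tests as local (troponin and urine pregnancy testing), which would be odd if every test were already local. Appendix 1 speaks of laboratory data transmitted electronically. On that reading, participants with a central pre-dose value are unaffected and only one protocol line is wrong. This stands as a real possibility. It does not remove the contradiction, because 8.2.6 names no central laboratory and does not override Appendix 2.

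A second reply is that the table in SAP 5.3 accepts the latest value up to Day 1 with no limit on source. That table deals with timing and does not lift the restriction in the text above it.

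A third reply is that the consequence is slight, and this is largely right. The analyses are descriptive. If everyone were affected, empty change tables would reveal the problem at first output. Out-of-range values still appear with reference ranges in Listings 24 and 25. Counting a missing grade as 0 also errs towards showing toxicity. What remains is the partial case, where the tables fill and the error is harder to see.

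A reader might also infer that the SAP plans to compare central baselines with local later values, since SAP 8.5 refers to all data being reported. That sentence concerns nominal visits and the absence of visit windows; it does not address laboratory source. Likewise, the rule "If there are multiple assessments on the same day, the mean will be used as the baseline value" might suggest mixing of laboratories, but nothing in the documents shows same-day values from two laboratories.

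**Conclusion.** The contradiction between SAP 5.3 and protocol Appendix 2 is certain, and the SAP has no rule that resolves it. Its effect is conditional. It arises only for participants without a central pre-dose value, and their number is unknown. It also assumes that their post-baseline results enter the tables, since SAP 5.3 attaches its source condition to baseline alone.

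For such participants, two tables lose change from baseline, two lack baseline range status (subject to the display standard), and two show a starting grade of 0, with an error of g grade steps for an unchanged abnormality of grade g.

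A reader might go further and conclude that all laboratory baselines are missing, or that the safety conclusions are unsound. The documents support neither. A central laboratory remains possible, and DLT, adverse event, response and PK results do not use this rule. The point is minor: confidence is high in the mismatch and low in the size of its effect.

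**What to change.** 1. Ask data management which laboratory supplied the protocol-required haematology and chemistry tests.
2. In SAP 5.3, replace the restriction to the central laboratory with the laboratory that performed the protocol-required test, so that a valid local baseline is used whenever no central value exists.
3. If a central laboratory was used, record that the statement about the local laboratory in Appendix 2 is incorrect. A note in SAP 2.1 or the study report would do. Amending the protocol itself would need ethics approval (protocol 10.1.1), after enrolment has already stopped (SAP 2.1).

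The grade-0 convention in SAP 8.5 can stay for baselines that are truly missing.

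The cost is one query and one changed phrase, plus one note if the laboratory was central. No new data are needed, and no endpoint or participant procedure changes.
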